## 5.4 Participant Disposition

Participant disposition will be summarized as follows:

- The number of participants who failed screening and the reasons for failure will be tabulated, by study part, for all participants.
- The number of participants, who entered the study, were randomized, and who are in each analysis set will be summarized by treatment group and overall for Part A, for the screened set.
- The number of early withdrawals and the reasons for withdrawals will be tabulated by treatment group and overall for Part A, for the full analysis set.

## 5.5 Protocol Deviations

Major protocol deviations will be summarized by code. A listing of protocol deviations will be provided within Appendix 16.2 of the clinical study report (CSR).

## 5.6 Baseline Comparability

The comparability of treatment groups with respect to participant demographics and baseline characteristics will be assessed in a descriptive manner. No formal statistical testing will be performed.

Standard continuous or categorical variable summaries will be presented by treatment group for the following variables based on the Safety Analysis Set.

- Demographic data
- Disease history
- Medical history

## 5.7 Medical History

Separate tabulations of previous and ongoing conditions at screening will be presented by treatment group and overall for the safety analysis set. Conditions will be presented by Medical Dictionary of Regulated Activities (MedDRA) primary system organ class (SOC) and preferred term (PT).

## 5.8 Prior and Concomitant Medications

Separate tabulations will be produced for prior and concomitant medications presented by treatment group and overall for the Safety Analysis Set. Prior medications are defined as all medications starting and stopping before the date of first dose of study drug. Concomitant medications are defined as medications taken on or after the date of first dose of study drug.

QMD Ref: Worldwide-TMP-ST-054-1.0_Effective: 12Aug2022	Governing QMD: Worldwide-SOP-ST-026
Confidentiality Statement This document is the property of Worldwide Clinical Trials Inc. and may not be duplicated, copied, altered or removed from company without prior approval from Worldwide Quality Assurance or in compliance with Worldwide Standard Operating Procedures.	

Worldwide Clinical Trials Controlled Quality Management Document		
 WORLDWIDE CLINICAL TRIALS	Sponsor:	Eli Lilly and Company
	Protocol Number:	J4N-MC-YFAA
STATISTICAL ANALYSIS PLAN		

Concomitant medications will be summarized using Anatomic Therapeutic Chemical (ATC) Level 2.

## 5.9 Pharmacokinetic Analyses

### 5.9.1 Concentration-Time Data

LY3885125 plasma concentration-time data will be tabulated by nominal time and treatment/dose level for single dose cohorts and by nominal time, study day, and treatment/dose level multiple dose cohorts using descriptive statistics. For presentation of the individual data and summary statistics, concentrations below the limit of quantitation (BLQ) will be set to zero. Nominal and relative time will be presented in hours.

LY3885125 plasma samples will be collected at:

#### Part A (Single Dose Cohorts):

Day 1: CCI hours postdose. Plasma samples may be collected during the monitoring extension at CCI hours postdose.

Mean plasma concentration-time data will be presented graphically on linear and semi-logarithmic scales using nominal times. Individual subject concentration-time data will be presented graphically on linear and semi-logarithmic scales using actual times. For individual subject concentration-time data, spaghetti plots (all subjects in one plot per treatment and study day) and all treatments in one plot for each subject will be created. The following concentration-time profiles will be created:

#### Part A (Single Dose Cohorts):

- Mean concentration-time profile comparing treatments/dose levels
- All subject concentration-time profiles for each treatment/dose level

Urine will be collected and tabulated by collection interval for Part A (single dose cohorts) during the following intervals: CCI hours post-dose for each period.

The PK Analysis Set will be used in the tabulation of concentration-time data and in the creation of concentration-time profiles. The Safety Analysis Set will be used for the concentration-time listings.

### 5.9.2 PK Methodology

Concentration-time data for LY3885125 in plasma and urine will be analyzed using noncompartmental methods in Phoenix™ WinNonlin® (Version 8.3.4.295 or higher, Certara,

QMD Ref: Worldwide-TMP-ST-054-1.0_Effective: 12Aug2022	Governing QMD: Worldwide-SOP-ST-026
Confidentiality Statement This document is the property of Worldwide Clinical Trials Inc. and may not be duplicated, copied, altered or removed from company without prior approval from Worldwide Quality Assurance or in compliance with Worldwide Standard Operating Procedures.	

Worldwide Clinical Trials Controlled Quality Management Document		
 WORLDWIDE CLINICAL TRIALS	Sponsor:	Eli Lilly and Company
	Protocol Number:	J4N-MC-YFAA
STATISTICAL ANALYSIS PLAN		

L.P.) in conjunction with Certara Integral™ (Version 24.4.2 or higher, Certara, USA, Inc.). The PK Analysis Set will be used in the PK analysis.

During the PK analysis, plasma and urine concentrations below the limit of quantification (BLQ) up to the time of the first quantifiable concentration will be treated as zero. Embedded (plasma values between 2 quantifiable concentrations) and terminal plasma BLQ concentrations will be treated as “missing”. Calculation of the PK characteristics in plasma will be based on actual elapsed times [h] relative to dosing, urine PK analysis will be based on collection interval.

At least 3 consecutive quantifiable concentrations are required to estimate AUClast. If a PK profile has at least 1 quantifiable concentration, then Cmax, and Tmax will be reported; other parameters will be reported as missing (ND).

### 5.9.3 Statistical Analysis

#### 5.9.3.1 Dose Proportionality

The PK parameters for LY3885125 Cmax, AUC0-24, AUClast, and AUCinf after single doses (Part A) will be compared across doses to assess dose proportionality (i.e., proportionality of a change in systemic exposure with a change in dose). Statistical analyses will be done using a power model with mixed effects (Smith, 2000) of the following general form:

$$\ln(\text{PK}) = \ln(\beta_0) + \beta_1 \cdot \ln(\text{Dose}) + \varepsilon,$$

Where

PK is the PK parameter tested (e.g. Cmax or AUC)

ln(β0) is the y-intercept,

β1 is the slope (a value of β1 ≈ 1 indicates linearity), and

ε is an error term

The estimate of slope, β1 will be reported along with the corresponding 2-sided 90% CIs. If the 90% CI of β1 includes 1 and the estimate of β1 is relatively close to 1, PK data may appear to be dose proportional. Dose proportionality plots will be created as well.

### 5.10 Pharmacodynamic Analyses

#### 5.10.1 PCSK9 and Apo Panel

Descriptive statistics of the observed values and change from baseline (continuous data) will be presented by treatment group and visit for PCSK9 and ApoB.

CCI [REDACTED]

[REDACTED]

QMD Ref: Worldwide-TMP-ST-054-1.0_Effective: 12Aug2022	Governing QMD: Worldwide-SOP-ST-026
Confidentiality Statement This document is the property of Worldwide Clinical Trials Inc. and may not be duplicated, copied, altered or removed from company without prior approval from Worldwide Quality Assurance or in compliance with Worldwide Standard Operating Procedures.	

Worldwide Clinical Trials Controlled Quality Management Document		
 WORLDWIDE CLINICAL TRIALS	Sponsor:	Eli Lilly and Company
	Protocol Number:	J4N-MC-YFAA
STATISTICAL ANALYSIS PLAN		

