Abbreviations: AE = adverse event; ApoB = apolipoprotein B; BP = blood pressure; COVID-19 = Coronavirus disease 2019; CRF = case report form; CRU = clinical research unit; D = day; ECG = electrocardiogram; ET = early termination; h = hour(s); FSH = follicle-stimulating hormone; HCV = hepatitis C virus; HDL-C = high-density lipoprotein cholesterol; I/E = inclusion/exclusion; ISR = injection-site reaction; LDL-C = low-density lipoprotein cholesterol; CCI min = minutes; P = predose; PCSK9 = proprotein convertase subtilisin/kexin type 9; PCR = polymerase chain reaction; PD = pharmacodynamics; PE = physical examination; PK = pharmacokinetics; PR = pulse rate; Q2W = once every 2 weeks; PUC = preparative ultracentrifugation; Q4W = once every 4 weeks; RR = respiration rate; SC = subcutaneous; TEAE = treatment-emergent AE; TG = triglyceride; VAS = visual analog score; VLDL-C = very low-density lipoprotein cholesterol.

- a All follow-up visits should take place in the morning after an overnight fast of at a minimum **CCI** hours. Water is permitted *ad libitum* during the fasting period.
- b After Day **CCI**, once any treatment related AEs are resolved and PCSK9 levels return to at least **CCI**% of baseline, the Monitoring Extension visits may be discontinued. The final visit of a participant who completes the study will be the first scheduled Monitoring Extension visit after they report no ongoing AEs, and after PCSK9 levels have returned to at least 80% of baseline in a blood sample collected at one of the preceding visits. At the participant's final visit, they will receive the assessments performed at ET, except for the collection of a blood sample for PCSK9 assessment.
- c Outpatient follow-up visits on Days **CCI** will be conducted through a remote telehealth visit assessing AE/concomitant medications.
- d On Day -1 prior to randomization review AEs, concomitant medications, and compliance to Inclusion/Exclusion criteria.
- e Discharge from CRU after all assessments have been completed.
- f All doses of study intervention will be administered SC in the morning after an overnight fast of approximately 8 hours duration.
- g Complete physical examination performed at Screening, ET and last visit., and symptom-directed examinations at all other visits.
- h Body weight is measured at any time before breakfast.

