### 3. Objectives and Endpoints

Objectives	Endpoints
Primary	
Part A: 
 
To determine the safety and tolerability of LY3885125 after a single SC dose in participants with dyslipidemia.
 
	
 
AEs.
 
Serious adverse events (SAEs).
 

Part B: 
 
To determine the safety and tolerability of LY3885125 after 2 SC doses on Days CCI in participants with NAFLD and elevated ALT.
 
	
 
AEs.
 
SAEs.
 

Secondary	
Part A: 
 
To assess the PK and PD of LY3885125 after a single SC dose.
 
	
 
LY3885125 area under the concentration-time curve (AUC), maximum observed concentration (<math>C_{max}</math>), time of <math>C_{max}</math> (<math>T_{max}</math>).
 
Changes in PCSK9 and apolipoprotein B (ApoB) from baseline relative to placebo.
 

Part B: 
 
To assess the PK and PD of LY3885125 following 2 SC doses on Days CCI.
 
	
 
LY3885125 AUC, <math>C_{max}</math>, <math>T_{max}</math>.
 
Relative change of liver fat content from baseline to Weeks CCI by magnetic resonance imaging proton density fat fraction (MRI-PDFF) compared with placebo.
 
Changes in PCSK9 and ApoB from baseline relative to placebo.
 

Objectives	Endpoints
Exploratory	

CCI [REDACTED]
 

• CCI [REDACTED]

	

• CCI [REDACTED]

• CCI [REDACTED]

• CCI [REDACTED]

CCI [REDACTED]
 

• CCI [REDACTED]

 

• CCI [REDACTED]

	

• CCI [REDACTED]

• CCI [REDACTED]

 

• CCI [REDACTED]

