**Table 4.3 Projected Human Dose Range Based on SCAP mRNA Knockdown and PCSK9 Inhibition-Based on Mouse and Monkey Models**

Human Dose (mg)	SCAP mRNA Knockdown Based on Mouse Model	Serum PCSK9 Inhibition Based on Mouse Model	SCAP Knockdown Based on Rhesus Monkey Model
[REDACTED]	[REDACTED]	[REDACTED]	[REDACTED]
[REDACTED]	[REDACTED]	[REDACTED]	[REDACTED]
[REDACTED]	[REDACTED]	[REDACTED]	[REDACTED]
[REDACTED]	[REDACTED]	[REDACTED]	[REDACTED]
[REDACTED]	[REDACTED]	[REDACTED]	[REDACTED]

Abbreviations: PCSK9 = proprotein convertase subtilisin/kexin type 9; SCAP = sterol regulatory element binding protein (SREBP) cleavage activating protein.

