19. CCI [REDACTED]
20. CCI [REDACTED]
21. Taken drugs associated with hepatic steatosis (e.g., amiodarone, valproic acid, methotrexate, tamoxifen) for more than 2 weeks in the 3 months prior to screening visit. Note: If the use of such drugs is anticipated to be medically necessary within the next 6 months, the participant should also be excluded
22. Receiving chronic CCI [REDACTED] systemic glucocorticoid therapy (excluding topical, intra ocular, intranasal, or inhaled preparations) or have received such therapy within 3 months prior to screening visit.
23. eGFR less than or equal to CCI [REDACTED], calculated by Chronic Kidney Disease Epidemiology (CKD-EPI) at screening.
24. Hypersensitivity to LY3885125 or to any of the excipients.
25. Any recent or recurrent infection within 14 days before dosing.
26. Type 1 diabetes mellitus or any other type of diabetes mellitus other than T2DM.
  - a. Poorly controlled T2DM with glycated hemoglobin (HbA1c) of CCI [REDACTED] is excluded.
27. Unwillingness to discontinue over-the counter (OTC) herbal medications that in the opinion of the Investigator can interfere with the study (see Section 6.9).

28. Initiation of an OTC medication in the 7 days prior to dose administration, or a new prescription medication in the 14 days prior to dose administration (including any medications for the treatment of obesity), except for hormone replacement therapy, vitamin and mineral supplements, low-dose aspirin, and occasional use of acetaminophen or ibuprofen. Additionally:
  - a. A stable dose of statin medication for at least 8 weeks prior to screening is allowed;
  - b. For participants with T2DM, stable treatment for at least 3 months prior to screening visit consisting of:
    - i. Either diet/physical activity alone; or
    - ii. Stable (CCI change) dose of basal insulin and/or oral antihyperglycemic medications (CCI); see Exclusion Criteria 19).
  - c. For participants with hypertension, a stable dose of up to 2 antihypertensive medications for CCI months prior to screening is allowed.
  - d. Hormone replacement therapy in postmenopausal women is allowed, but women must be on stable therapy for CCI months prior to screening.
  - e. If any medications (other than those that are specifically allowed) are taken, an otherwise suitable participant may be included following the agreement between the Investigator and the Sponsor.

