### 9.3. Statistical Analyses

#### 9.3.1. General Considerations

Statistical analysis of this study will be the responsibility of the Sponsor or its designee. Details of statistical analysis methods will be described in the Statistical Analysis Plan (SAP).

Bayesian analyses will be performed using the primary PD marker – change from baseline in PCSK9 in Part A and relative change of liver fat content (percent) by MRI-PDFF in Part B at Weeks CCI . All other analyses will only provide descriptive statistics tabulated by cohort. Some descriptive summaries, e.g., participant accounting, study disposition, and participant demographics, will also provide descriptive statistics for all cohorts pooled together.

Incidence based summaries and analyses with binomial outcomes will use all observed data for participants in the respective analysis set with presentation of number and percent of participants.

Summaries for continuous variables will include the number of participants in the analysis, mean, standard deviation, median, minimum, and maximum.

Any change to the data analysis methods described in the protocol will require a protocol amendment ONLY if it changes a principal feature of the protocol. Any other changes to the data analysis methods described in the protocol, and the justification for making the change, will be described in the SAP or clinical study report (CSR).

Handling of missing, unused, and spurious data will be addressed in the SAP, where appropriate. Adjustments to the planned analyses will be described in the final CSR.

SAS software version 9.4 or higher will be used to perform statistical analyses, unless otherwise specified.

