	14.3.4.6.3	Safety ECG Data, Overall Interpretation Shift from Baseline to Worst Post Baseline, Part A – Safety Analysis Set	IP	-
	14.3.4.7.1	Prior Medications by ATC Level 3 and Preferred Name, Part A – Full Analysis Set	IP	-
	14.3.4.7.2	Concomitant Medications by ATC Level 3 and Preferred Name, Part A – Full Analysis Set	IP	14.3.4.7.1
	14.3.4.8.1	PCSK9 Data, Descriptive Statistics for Observed Values and Change from Baseline, Part A – PD Analysis Set	IP	-
	14.3.4.8.2	Apo Panel Data, Descriptive Statistics for Observed Values and Change from Baseline, Part A – PD Analysis Set	IP	14.3.4.8.1
	14.3.4.8.3	CCI [REDACTED] [REDACTED] [REDACTED] – [REDACTED]	IP	14.3.4.8.1
	14.3.4.9	Linear Mixed-Effects Model for Plasma PK Concentrations of LY3885125 and ΔQTcF, Part A – PK Analysis Set	Stat IP	-
	14.3.4.10	Summary of Immunogenicity Parameters by Treatment Group – Immunogenicity Analysis Set	IP	-
14.4.1	PK Analysis			
	14.4.1	Descriptive Statistics for Concentration-Time Data of LY3885125 in Plasma after Single Ascending Subcutaneous Doses of LY3885125 – PK Analysis Set	IP	-

QMD Ref: Worldwide-TMP-ST-054-1.0_Effective: 12Aug2022	Governing QMD: Worldwide-SOP-ST-026
Confidentiality Statement This document is the property of Worldwide Clinical Trials Inc. and may not be duplicated, copied, altered or removed from company without prior approval from Worldwide Quality Assurance or in compliance with Worldwide Standard Operating Procedures.	

Worldwide Clinical Trials Controlled Quality Management Document		
 WORLDWIDE CLINICAL TRIALS	Sponsor:	Eli Lilly and Company
	Protocol Number:	J4N-MC-YFAA
STATISTICAL ANALYSIS PLAN		

Section Number	Table Number	Table Title	Validation Method	Shell Number (if repeat)
	14.4.2	LY3885125 Plasma Pharmacokinetic Parameters after Single Ascending Subcutaneous Doses of LY3885125 – PK Analysis Set	IP	-
	14.4.3	Amount of LY3885125 Excreted in Urine per Collection Interval – PK Analysis Set	IP	-
	14.4.4	Percentage of LY3885125 Dose Excreted in Urine per Collection Interval – PK Analysis Set	IP	-
	14.4.5	LY3885125 Urine Pharmacokinetic Parameters after Single Ascending Subcutaneous Doses of LY3885125 – PK Analysis Set	IP	-
	14.4.6	Dose-Proportionality Assessment of LY3885125 in Plasma after Single Ascending Subcutaneous Doses of LY3885125 – PK Analysis Set	MR	-

QMD Ref: Worldwide-TMP-ST-054-1.0_Effective: 12Aug2022	Governing QMD: Worldwide-SOP-ST-026

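### The PD tables for PCSK9 and ApoB plan no participant-level percent change from baseline; adding it would give a more precise Part A dose-response description at almost no cost.

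*SAP*

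**What the plan says.** SAP 5.10.1 gives the planned summary for both markers: "Descriptive statistics of the observed values and change from baseline (continuous data) will be presented by treatment group and visit for PCSK9 and ApoB". The list of tables in SAP section 10 repeats it: "PCSK9 Data, Descriptive Statistics for Observed Values and Change from Baseline, Part A" (Table 14.3.4.8.1) and "Apo Panel Data, Descriptive Statistics for Observed Values and Change from Baseline, Part A" (Table 14.3.4.8.2). SAP 5.3 adds n, mean, median, SD, minimum and maximum, by dose and for pooled placebo. Listing 16.2.8.10 gives individual PD data.

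The secondary endpoint in Protocol section 3 is "Changes in PCSK9 and ApoB from baseline relative to placebo". Protocol 9.3.1, naming the primary PD marker of each part, puts two wordings side by side: "change from baseline in PCSK9 in Part A and relative change of liver fat content (percent) by MRI-PDFF in Part B".

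Elsewhere the protocol reads PCSK9 against the participant's own baseline. Footnote b to the Part A schedule (Protocol 1.3.1) lets a participant finish "after PCSK9 levels have returned to at least 80% of baseline in a blood sample collected at one of the preceding visits". Table 4.3 has a column headed "Serum PCSK9 Inhibition Based on Mouse Model", and Protocol 4.3.3 expresses the projected SCAP mRNA effect as a percent reduction. The figures themselves are blacked out in both places.

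**The concern.** The drug acts by knocking down hepatic mRNA, and the protocol's dose rationale and follow-up rule describe the effect as a fraction of baseline. If that is right, a participant's absolute fall is the percent fall multiplied by that participant's own baseline. Two cohorts with the same percent fall but different mean baselines will show different mean absolute changes.

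Randomisation does not remove such differences between doses. Cohorts are enrolled one after another, and allocation is random only between drug and placebo within a cohort. Each dose has 6 or 9 active participants. Protocol 5.2, exclusion criterion 28a, is a possible source of baseline spread: "A stable dose of statin medication for at least 8 weeks prior to screening is allowed".

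At stake is how precisely the final tables describe the PCSK9 dose-response, which is the main PD result of the only part of the study that was run.

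**Working it through.** **Cohort sizes.** The allocation ratios in Protocol 4.1.1 give 2×(6+2) + 3×(9+2) + (10+9) = 16 + 33 + 19 = 68, which reproduces the approximate Part A total in Protocol 9.5. Cohort 6 was not enrolled (SAP section 3). Cohorts 1 to 5 therefore have 6, 6, 9, 9 and 9 active participants (39) and 10 on placebo.

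**Assumed inputs.** The documents give no mean, variance or effect size for PCSK9 or ApoB. Assumed are: a proportional effect; true falls r of 40% and 55% at adjacent doses; log-normal baselines with between-person CV c of 25-45%; and independent within-person CV w of 15-20% at baseline and at follow-up.

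**Absolute change.** With mean baseline scaled to 1, the variance of one participant's change is

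V(r) = r²c² + w²[1 + (1−r)²](1 + c²)

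and P(wrong order) ≈ 1 − Φ(0.15 / √{[V(0.40) + V(0.55)]/n}).

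- n = 9, c = 0.25, w = 0.15: V(0.40) = 0.0425 and V(0.55) = 0.0477. The SE is √(0.0902/9) = 0.100, z = 1.50, P = 6.7%.
- n = 9, c = 0.45, w = 0.20: V(0.40) = 0.0978 and V(0.55) = 0.1191. The SE is √(0.2169/9) = 0.155, z = 0.97, P = 16.7%.

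**Percent change.** The baseline cancels, and the variance is about 2w²(1−r)². Summed over the two doses this is 2w²(0.36 + 0.2025) = 1.125w².

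- n = 9, w = 0.15: SE = √(0.0253/9) = 0.053, z = 2.83, P = 0.2%.
- n = 9, w = 0.20: SE = √(0.0450/9) = 0.071, z = 2.12, P = 1.7%.

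**Log ratio, the scale proposed below.** The true difference is ln(0.60/0.45) = 0.288 and the SE is √(4s²/n), with s² = ln(1 + w²). At n = 9, z = 0.288/0.099 = 2.89 (P = 0.2%) for w = 0.15, and 0.288/0.132 = 2.18 (P = 1.5%) for w = 0.20.

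**Simulation.** 40,000 replicates under the same assumptions agree with the formulas. Probability of wrong order:

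| Summary | n = 6 per dose | n = 9 per dose |
|---|---|---|
| Mean absolute change | 11-21% | 7-16% |
| Mean percent change | 1-4% | 0.2-2% |
| Group mean change ÷ group mean baseline | 1.1-4.9% | 0.2-2.3% |

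The relative standard error of the mean effect at the higher dose, n = 9, is 13-21% on absolute change and about 6-8% on either of the other two.

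**Sensitivity to the spacing of effects** (n = 9, w = 15%, c = 20-50%):

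- 40% against 50%: wrong order 14-23% on absolute change, about 3.5% on percent change.
- 30% against 50%: 1.5-6.3% on absolute change, 0.1% or less on percent change.

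Without within-person noise, the order reverses only if the lower-dose cohort's mean baseline exceeds the other's by the ratio of the true falls: 0.50/0.40 = 1.25 in the first case and 0.50/0.30 = 1.67 in the second. The risk is material when neighbouring effects are close and small when they are far apart.

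**The case against.** The strongest reply is that the planned tables already hold the relative effect. Observed values at baseline and at each visit stand beside the change, so the group percent fall is one division. The third row of the simulation table shows that this recovers nearly all the gain. This stands, with three limits. The SAP does not plan the ratio. It needs the same participants at both time points. And its between-participant SD or CV cannot be obtained from the tables, because it needs each participant's paired values; the listing allows only ad hoc calculation.

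Several stronger readings are tempting, and the documents do not support them.

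- A reader might infer that results appear only as absolute change, or cannot be compared with Table 4.3 or the 80% level. Observed values are tabulated and individual data are listed, so both comparisons can be made by hand.
- A reader might infer a departure from the protocol. The protocol words the PCSK9 endpoint simply as change from baseline and reserves the percent scale for liver fat, a Part B endpoint. The SAP follows that wording.
- A reader might infer that a Part B dose hangs on this. SAP sections 1 and 2 say the study stopped after Cohort 5 and will not proceed to Part B.
- A reader might infer that the dose order will be reversed, or that every group mean is distorted. Reversal depends on assumed figures, and pooled placebo, with expected change near zero, is scarcely affected.
- Criterion 28a permits stable statin use but does not show the mix actually enrolled.

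Blacked-out text follows the sentence in SAP 5.10.1. The contents list places 5.10.2, on Lp(a), next, and the visible table titles agree with the quoted sentence. Hidden percent-change text for PCSK9 is unlikely but cannot be excluded.

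**Conclusion.** The point holds as a free improvement to descriptive tables. The readable SAP plans no participant-level percent change or ratio to baseline, while the protocol's recovery rule and dose rationale treat PCSK9 relative to baseline. If the effect is proportional, mean absolute change is the noisier guide to dose order, with a relative standard error roughly two to two and a half times as large (13-21% against 6-8%, n = 9).

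The conclusion rests on proportionality and on assumed CVs and effect sizes. The direction was the same in every scenario run; the size was not. For ApoB the argument is by extension only, since no visible passage handles it as a percentage of baseline. What is gained is a more precise and more readable account of the Part A dose-response.

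**What to change.** In SAP 5.10.1 and Table 14.3.4.8.1, add percent change from baseline in PCSK9 by dose, pooled placebo and visit. For each participant with both values, take ln(visit value / baseline value). Summarise on the log scale, and back-transform to a geometric mean percent change, 100×[exp(mean) − 1], with the geometric CV of the ratio. Keep the observed-value and absolute-change rows, and amend the table title. Do the same for ApoB in Table 14.3.4.8.2 for consistency.

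The cost is a sentence in the SAP, one derived variable and extra rows in two existing tables. It needs no new data and no change to the protocol endpoint. SAP section 5 provides for amendments approved before the Part A database lock and for a documented addendum after it.

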## 9. Statistical Considerations

### 9.1. Statistical Hypotheses

No inferential analyses are planned for either Part A or Part B, so no formal statistical hypotheses are defined. Only descriptive summary statistics will be provided for endpoints of interest.

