### **9.3.3. Secondary Endpoint(s) Analysis**

The secondary endpoints in Part A are:

- PK - LY3885125 AUC, Cmax, Tmax.
- PD - Changes in PCSK9 and ApoB from baseline relative to placebo.

The secondary endpoints in Part B are:

- PK - LY3885125 AUC, Cmax, Tmax.
- PD - Relative change of liver fat content (percent) from baseline to CCI by MRI-PDFF compared to placebo.
- PD - Changes in PCSK9 and ApoB from baseline relative to placebo.

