## 2 STUDY OBJECTIVES AND ENDPOINTS

Part A primary objective: To determine the safety and tolerability of LY3885125 after a single SC dose in participants with dyslipidemia.
Endpoint(s):

 
Adverse events (AEs).
 
Serious adverse events (SAEs).
 

Analysis set: Safety analysis set

Part A secondary objective: To assess the PK and PD of LY3885125 after a single SC dose.
Endpoint(s):

 
LY3885125 area under the concentration-time curve (AUC), maximum observed concentration (<math>C_{max}</math>), time of <math>C_{max}</math> (<math>T_{max}</math>).
 
Changes in proprotein convertase subtilisin/kexin type 9 (PCSK9) and apolipoprotein B (ApoB) from baseline relative to placebo.
 

Analysis set: PK analysis set

Part A exploratory objective: To assess the effect of LY3885125 CCI [REDACTED] and immunogenicity.
Endpoint(s):

 
Changes in CCI [REDACTED] from baseline relative to placebo.
 
Changes in CCI [REDACTED] from baseline relative to placebo.
 
Prevalence of standard immunogenicity statuses.
 

Analysis set: PD analysis set

Part B objectives and endpoints are excluded from this SAP as the study will not proceed to Part B.

Worldwide Clinical Trials Controlled Quality Management Document		
 WORLDWIDE CLINICAL TRIALS	Sponsor:	Eli Lilly and Company
	Protocol Number:	J4N-MC-YFAA
STATISTICAL ANALYSIS PLAN		

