## 8 CHANGES TO PLANNED PROTOCOL ANALYSIS

There are no changes to the planned protocol analysis.

Worldwide Clinical Trials Controlled Quality Management Document		
 WORLDWIDE CLINICAL TRIALS	Sponsor:	Eli Lilly and Company
	Protocol Number:	J4N-MC-YFAA
STATISTICAL ANALYSIS PLAN		

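### The readable SAP plans no placebo-relative estimate for the PCSK9 and ApoB endpoint, omits the protocol's Bayesian PCSK9 analysis without recording it, and labels the endpoint with conflicting analysis sets

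*SAP*

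**What the plan says.** **Endpoint.** Protocol 9.3.3 lists it as "PD - Changes in PCSK9 and ApoB from baseline relative to placebo". SAP Section 2 carries the same endpoint, ending "and apolipoprotein B (ApoB) from baseline relative to placebo".

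**Planned analysis in the SAP.** Section 5.10.1: "Descriptive statistics of the observed values and change from baseline (continuous data) will be presented by treatment group and visit for PCSK9 and ApoB". Section 5.3 limits continuous summaries to n, mean, median, SD, minimum and maximum, in columns for each dose, pooled LY3885125 and pooled placebo. The output list in Section 10 has one PCSK9 table, "PCSK9 Data, Descriptive Statistics for Observed Values and Change from Baseline, Part A – PD Analysis Set", and an Apo panel table (14.3.4.8.2) of the same form.

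**Planned analysis in the protocol.** Section 9.3.1: "Bayesian analyses will be performed using the primary PD marker – change from baseline in PCSK9 in Part A". It adds that all other analyses are descriptive. Section 9.1, however, rules out inferential analyses and says: "Only descriptive summary statistics will be provided for endpoints of interest". Section 9.3.1 also requires changes of method, with their justification, to be described in the SAP or the clinical study report.

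**Declared changes.** SAP Section 8: "There are no changes to the planned protocol analysis".

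**Analysis set.** SAP Section 2 puts one line under the combined PK and PD secondary objective: "Analysis set: PK analysis set". Section 5.1.5 restricts that set to participants dosed with LY3885125. Section 5.1.4 and protocol 9.2 assign PD endpoints to the PD analysis set, and Tables 14.3.4.8.1 and 14.3.4.8.2 and Listing 16.2.8.10 follow them.

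**The concern.** The endpoint is a comparison, and the plan summarises its two sides without making the comparison. PCSK9 matters here: protocol 4.2 makes it the marker by which the drug's effect in Part A is judged. As Part B will not proceed, Part A is the only human evidence on it from this trial.

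Three things are at stake:

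- If the SAP is followed exactly, the report contains no pre-specified estimate of drug effect against placebo. A contrast formed later would have its scale, time point and interval chosen with the data in view.
- An analysis that the protocol says will be performed disappears while the SAP states that nothing changed, so the study report has no trace of the decision.
- Someone programming from Section 2 alone would use a population in which the comparison cannot be formed.

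**Working it through.** **1. Is a placebo contrast planned anywhere readable?** In the SAP text and Section 10:

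- 5.10.1 and 5.3: per-group summaries only.
- Tables 14.3.4.8.1 and 14.3.4.8.2: descriptive titles.
- Table 14.3.4.8.3: title blacked out, but it reuses the shell of the descriptive PCSK9 table.
- Outputs identified as models: the concentration-QTcF mixed model (14.3.4.9) and dose proportionality (14.4.6). Neither concerns PCSK9 or ApoB.
- Figures: none for PD.

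A blacked-out block follows the quoted sentence in 5.10.1. The contents page places 5.10.2, Lp(a), there.

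**2. Is the Bayesian analysis accounted for?** Protocol 9.3.1 names two: PCSK9 in Part A and liver fat in Part B. Dropping Part B explains the second. It does not explain the first, because SAP Section 1 says the study stopped after Cohort 5 was completed.

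**3. How many participants could be compared?** The only related figure that can be reproduced is the planned Part A total of about 68 in protocol 9.5. Reading each allocation ratio as the cohort's count:

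2 × (6 + 2) + 3 × (9 + 2) + (10 + 9) = 16 + 33 + 19 = 68.

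It matches. Cohort 6 was not enrolled, which leaves:

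- active: 6 + 6 + 9 + 9 + 9 = 39
- placebo: 5 × 2 = 10
- total: 49

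Placebo on the PD set: up to 10. Placebo on the PK set: 0.

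The SAP Section 4 table shows 30 for Cohorts 1 and 2 in the public copy. That does not fit the protocol total, since 30 + 30 + 19 = 79 already exceeds 68. I treat it as an artefact of redaction.

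**4. How precise would the contrast be?** SE = SD × √(1/k + 1/10), for k active participants against pooled placebo. With six groups and a pooled SD, df = 49 − 6 = 43, and the two-sided 90% t quantile is about 1.681.

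| k | √(1/k + 1/10) | 90% half-width | Factor, log SD 0.25 | Factor, log SD 0.45 |
|---|---|---|---|---|
| 6 | 0.516 | 0.87 SD | ×/÷ 1.24 | ×/÷ 1.48 |
| 9 | 0.459 | 0.77 SD | ×/÷ 1.21 | ×/÷ 1.42 |

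Each factor is exp(1.681 × SE). The log-scale SDs are an assumed range; the documents give none.

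**5. What would baseline adjustment gain?** If baseline and follow-up have equal variance and correlation ρ, the variance under adjustment is (1 + ρ)/2 of that of the plain change score: 0.65, 0.75 and 0.85 for ρ = 0.3, 0.5 and 0.7. That is a saving of 15% to 35%. Equal variance and the range of ρ are also assumptions.

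**6. Does the 10 hold at every visit?** Not necessarily. Under footnote b of the Part A schedule (protocol 1.3.1), extension visits may end once related AEs have resolved and PCSK9 has recovered towards baseline. Placebo participants would probably meet that condition first. Late visits may then have fewer than 10 placebo participants, and active arms increasingly made up of those still suppressed.

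**The case against.** The strongest defence is that this is a small Phase 1 trial with safety as its primary endpoint, that protocol 9.1 promises descriptive statistics only, and that the SAP delivers them with a pooled placebo column. Part of this stands. The SAP agrees with one protocol section while departing from another, and protocol 9.3.1 allows the change to be justified in the clinical study report. But 9.3.1 names PCSK9 as the exception to description, and a statement of no changes is wrong against that section. Nor does the SAP hold to description only: it plans 90% intervals for dose proportionality and for the QTcF model.

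A reader might infer more than the documents support:

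- **That the contrast is never computed.** Text after the quoted sentence is blacked out. It is probably Lp(a), but the claim must stay at the readable SAP.
- **That placebo is excluded from the analysis.** The Section 2 label conflicts with 5.1.4 and the tables, and those include placebo.
- **That no uncertainty is reported.** Per-arm n, mean and SD are planned, and an unadjusted difference and interval can be derived from them. What is missing is the pre-specified contrast.
- **That absolute change is the wrong scale.** The protocol's percent-of-baseline wording for PCSK9 is a rule for ending visits. For the endpoint it writes plain change, and keeps relative percent change for liver fat.
- **That Part B dose or interval selection is at risk.** SAP Section 2 says Part B will not proceed.
- **That a repeated-measures model on the log scale is required.** Neither document specifies one. It is one option.

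**Conclusion.** The point holds for the readable SAP. Three defects stand: a comparative endpoint without a planned comparison, a protocol analysis omitted under a declaration of no changes, and an internal contradiction on the analysis set. It should be fixed, but it does not threaten the primary safety objective or any dosing decision still open.

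The comparison that goes unreported is up to 10 pooled placebo participants against arms of 6 or 9. Its 90% interval would be about ×/÷ 1.21 at best and ×/÷ 1.48 at worst. This rests on the ratios being the cohort counts, complete data at the visit analysed, and the assumed log-scale SD of 0.25 to 0.45. The intervals are wide. With no effect size readable in the documents, I make no claim about what they could detect. The three defects do not depend on these figures.

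**What to change.** 1. **SAP Section 2.** Split the analysis-set line: PK analysis set for AUC, Cmax and Tmax; PD analysis set for PCSK9 and ApoB.
2. **SAP 5.10.1.** Add a placebo-adjusted estimate of change for each dose group against pooled placebo, adjusted for baseline, with a 90% interval. For PCSK9 this can be the protocol's Bayesian model, with its prior stated and a credible interval, or a simple frequentist model. For ApoB a simple frequentist model is enough. Name the scale (absolute, or log with percent change) and the main time points in advance. Say that late extension visits may have few placebo participants because exit depends on PCSK9 recovery, and keep the main time points clear of them.
3. **SAP Section 8.** Record whether the Bayesian PCSK9 analysis is kept or dropped, and why, and note the conflict between protocol 9.1 and 9.3.1.

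The cost is SAP wording and one additional table per marker. No new data are needed. SAP Section 5 requires amendments to be approved before Part A database lock; after that, the change belongs in a post-lock addendum and the contrast is no longer pre-specified.
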